1.4.2. Measures

Collected measures include demographics, baseline disease information, the primary outcome measure, the secondary outcome measures, the exploratory outcome measures, and app use information.

The primary outcome measure was chosen because it is the clinical measure that the app is intended to affect. Secondary measure 1 was chosen because it is the most common way of assessing preterm birth risk in similar trials. The other secondary measures are common clinical or operational measures of outcomes that components of the app intend to affect.

1.5. Sample Size Justification

Due to the observational nature of the study and recruitment context, it was not possible to predetermine the sample size based on statistical power for estimating the primary and secondary outcomes. Instead, all participants who met the inclusion criteria between September 2019 and February 2022 were included. The final sample has 12,344 deliveries, divided between the MHP and usual care cohorts (with 7147 in one and 5197 in the other, with their identities currently blinded). This represents about 12,287 different participants (we only have information about the percent of multiple deliveries for participants who downloaded the app, 0.464%). Given the sample sizes in the two cohorts, there is 80% power to detect an effect size of 0.051 days. Assuming that the outcomes are normally distributed with a standard deviation of 10 days (1), the study has 80% power to detect a 0.51 day difference in gestational age at birth between the cohorts.

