A Blinded Evaluation of the Effectiveness and Efficacy of the MyHealthyPregnancy Application Statistical Analysis Plan

This study will evaluate the effectiveness and efficacy of the MyHealthyPregnancy App, an app designed to reduce preterm birth risk. This study will use observational cohort data collected at the University of Pittsburgh Medical Center between September of 2019 and February of 2022.

July 18, 2022

[name], [name]

1. Description of the study

MyHealthyPregnancy (MHP) was developed using decision science principles to help prevent preterm birth. An observational cohort trial was conducted at the University of Pittsburgh Medical Center starting in September of 2019 until February 2022. This trial compares the effectiveness of MHP to usual care for pregnant people who delivered at the University of Pittsburgh Medical Center (UPMC). Patients at UPMC were able to download the MHP app after receiving a prescription for the app, as indicated by an EHR variable. Those who were prescribed the app and downloaded it were in the *MHP cohort*. Those who were prescribed the app and did not download it were in the *usual care cohort*. Prescriptions were offered to pregnant people by their care team at an early prenatal visit at UPMC.

EHR data is available for both cohorts of patients. It is the source of all measures, unless otherwise noted.

A linear effects model will be used to evaluate effectiveness by estimating the average treatment effect for the primary endpoint, preventing preterm birth risk.

For each dependent measure, these models will control for primary predictors, as identified in the research literature, that are available in the EHR.

A dose-response model will be used to estimate the effects of continuous measures of non-adherence (as opposed to dichotomous non-adherence, such as not initiating app use). Multiple measures of adherence will be analyzed, including measures of daily use, weekly use, time to initiation, and time from discontinuation to birth.

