1.4. Data collection

1.4.1. Eligibility Screening

Participants were included in the study if they were offered a prescription for MyHealthyPregnancy, were at least 18 years of age, pregnant, received care at UPMC, and delivered at a UPMC hospital.

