2.4. Loss to follow-up and other missing data

Given data-sharing constraints with UPMC, outcome data is available only for participants who delivered at UPMC hospitals. LH will report how many people downloaded the app and did not deliver at UPMC. This will allow us to estimate the percentage of participants lost due to delivering out of the system.

For included participants, there is a very little missing data for the primary measure (80/13752=0.06%). We will assume that such data is missing at random and exclude participants whose data is missing for a measure from analyses involving that measure. There is no missing data for the secondary measures. The same practice will be followed for the exploratory outcomes. No imputation will be done for any outcome measures.

Missing categorical values for baseline covariates (baseline disease information and demographics) will not be imputed, but treated as an additional category. Continuous variables missing less than 5% of the data will be imputed with the median value for that variable. Two continuous baseline covariates are missing more than 5% of data ADI_NATRANK (1330/13752=9.7%) and PREGRAVID_WEIGHT (1318/13752=9.6%). For these two variables, scatterplots and Little's test will be used to investigate if the data is missing completely at random (MCAR), missing at random (MAR), or missing not at random (MNAR) on 20% of the unblinded data. If the data appears to be MCAR or MNAR, median imputation will be used. If the data is MAR, multiple imputation will be used. If multiple imputation is needed, LH will generate data for the missing values so that EG remains blinded. For all missing data, we will conduct

sensitivity analyses, repeating analyses of primary and secondary outcomes using imputed values two standard deviations above and below the median. See Appendix A for the full list of collected baseline covariates.

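### If the September 2019 to February 2022 window bounds deliveries, late pregnancies enter only if they ended early, and the primary and propensity-score analyses have no guard against a changing download share

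*SAP*

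**What the plan says.** Eligibility (SAP section 1.4.1) requires an app prescription offer and that participants "were at least 18 years of age, pregnant, received care at UPMC, and delivered at a UPMC hospital". Section 1.5 adds that "all participants who met the inclusion criteria between September 2019 and February 2022 were included" and counts the sample in births: "The final sample has 12,344 deliveries, divided between the MHP and usual care cohorts". The opening summary gives the same months for the data, described as "observational cohort data collected at the University of Pittsburgh Medical Center between September of 2019 and February of 2022". Section 2.4 notes that "outcome data is available only for participants who delivered at UPMC hospitals". Entry comes months before the outcome: "Prescriptions were offered to pregnant people by their care team at an early prenatal visit at UPMC" (section 1).

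The primary outcome is gestational age at birth, compared as a mean (section 3.1). Date of first visit is left out of the primary outcome model (section 3.1.1) and of the propensity score model (section 3.1.5). It is added to each model in one sensitivity analysis (section 3.1.5, time effects), with no functional form stated. The SAP sets no limit on due date or first-visit date, and it does not report the download share over time.

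**The concern.** A cohort closed on a delivery date is truncated on the right. Among pregnancies that began late in the window, only those that ended before the cut-off are seen, so short gestations are over-represented among the latest first visits. Because the primary outcome is gestational length itself, the selection acts directly on it.

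Truncation alone does not bias the comparison. If the download share is the same throughout, the early births fall on both cohorts in proportion. If the share rose, more of them fall on the MHP cohort and the app looks harmful. If it fell, the app looks beneficial. Adjustment for baseline risk factors does not remove this, because the selection runs through calendar time and the outcome. Section 1.3 says the authors do not know directly how prescriptions were decided or whether downloading was encouraged, and section 3.1.5 names the pandemic as an outside influence, so a constant share cannot simply be presumed.

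**Working it through.** **The SAP's own figure.** Inputs from sections 1.5 and 3.1: cohorts of 7147 and 5197, SD 10 days, 5% level (two-sided assumed), 80% power.

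- √(1/7147 + 1/5197) = 0.01823
- (1.960 + 0.842) × 0.01823 = 0.0511 SD, or 0.511 day at SD 10. The stated 0.51 day reproduces. The 0.051 that section 1.5 labels as days is in SD units.
- Standard error of the difference: 10 × 0.01823 = 0.18 day.

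**Share of deliveries affected.** Assumptions: a 911-day window, first visit at 7 to 15 weeks (midpoint 77 days), and mean gestation 0.92 × 276 + 0.08 × 245 = 273.5 days. A delivery could still have been pregnant at the cut-off if 42 weeks (294 days) fell after it.

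- Average exposed time: 294 − 273.5 = 20.5 days
- Effective entry period: 911 − (273.5 − 77) = 714.5 days
- 20.5 / 714.5 = 2.9%, the same as by simulation.

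**Spurious difference with no app effect.** Simulation of 6 million pregnancies with even starts over a 913-day window and first visit near 70 days. A pregnancy is included if the first visit falls on or after the opening date and delivery on or before the closing date. Two assumed gestational-age distributions are used: Normal(275, 10), and an early-tail mixture (92% Normal(276, 8), 8% Normal(245, 20)). The restriction keeps pregnancies that started at least 300 days before the cut-off. Entries are MHP minus usual care, in days.

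| Download share | Distribution | No date term | Linear date term | Restricted |
|---|---|---|---|---|
| Rise 48% to 68% | Normal | −0.045 | 0.000 | −0.001 |
| | Early tail | −0.077 | 0.000 | −0.001 |
| Rise 38% to 78% | Normal | −0.089 | 0.000 | −0.002 |
| | Early tail | −0.152 | 0.000 | −0.002 |
| Fall 68% to 48% | Normal | +0.046 | 0.000 | +0.001 |
| | Early tail | +0.079 | 0.000 | +0.001 |
| Step 55% to 75%, last 300 days | Normal | −0.100 | −0.060 | −0.001 |
| | Early tail | −0.165 | −0.095 | −0.001 |
| Step 55% to 75%, last 240 days | Normal | −0.107 | −0.090 | 0.000 |
| | Early tail | −0.176 | −0.147 | 0.000 |

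A constant share gives 0.00. In the scenarios tabled, preterm birth shifts by 0.05 to 0.27 percentage points.

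**Other assumptions.**

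- A separate simulation using the 42-week rule gives, in absolute size, 0.04 to 0.11 day for a drift from 50% to 70%, 0.13 to 0.25 for 30% to 90%, and 0.08 to 0.19 for a late 20-point step. After the step, date adjustment leaves about 0.05 to 0.13. The restriction brings every case to about 0.02 or less and keeps about 97% of deliveries.
- If the start of the window is also set by delivery date, pregnancies that began before it enter only if they ended late, which adds to the bias. The largest case (30% to 86%, early tail) is then −0.32 day.
- If the window bounds only the first visit and all deliveries are followed up, the difference is within about 0.01 day of zero.

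**Against the target.** 0.04 / 0.51 = 8% and 0.25 / 0.51 = 49%. In standard errors, 0.04 / 0.18 = 0.2 and 0.25 / 0.18 = 1.4.

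**The case against.** The premise is an inference. Section 1.5 dates the meeting of several criteria together and does not name delivery as the dated event. The SAP is dated July 2022, so deliveries after February may have been captured. Section 2.4 uses a denominator of 13,752 against the final 12,344. The 1,408 records between them may have gone in a step the text does not describe, and the flow figure is not shown. This stands: the cut-off is the natural reading, not a stated fact. It does not remove the point, because no stated rule prevents the truncation.

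The bias also needs a changing download share, and the SAP gives no evidence of one. This stands too. The drift figures are illustrations.

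The strongest objection is that the SAP already plans a check. A reader might infer that truncation would spoil the first-visit-date sensitivity analysis as well. The SAP gives no ground for that. Under a linear trend a linear date term removes nearly all of the bias and does about as well as the restriction. It falls short only after an abrupt late change. The main models still omit date.

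Finally, the effect is small beside the self-selection into downloading. That is fair, and it limits the weight of the point.

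**Conclusion.** The concern holds in a limited form. Sections 1.4.1 and 1.5 together imply a delivery cut-off at February 2022. On that reading the primary and propensity-score analyses are open to a spurious difference of roughly 0.04 to 0.25 day if the download share moved over calendar time. The size rests on the assumed drift, the assumed gestational-age distributions and even entry over time. It is zero with a constant share and about zero if February 2022 bounds only prescriptions with complete follow-up.

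A reader might conclude that the primary result is compromised. The SAP does not support that: drift is undocumented, and no scenario reached 0.51 day, including the −0.32 day case with both ends of the window set by delivery. This is a minor point, worth acting on because the remedy is cheap and the direction of any bias cannot be known in advance.

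**What to change.** 1. State in section 1.5 which event the window applies to at each end (prescription, first visit or delivery), and the date to which deliveries were captured.
2. If the closing date bounds deliveries, restrict the analysis set to pregnancies for which PREG_CONTACT_DATE + (294 − GESTAGE_ATVISIT_DAYS) falls on or before the cut-off. At minimum, report this as a sensitivity analysis for gestational age and preterm birth. It assumes that both Appendix A variables refer to the same visit, which the SAP should confirm.
3. Report the download share by month of first visit once the cohorts are unblinded, so that readers can see whether the condition for bias was met.

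Cost: SAP wording and about 3% of deliveries (12,344 × 0.029 ≈ 360). The detectable difference goes from 0.511 to 0.511 / √0.971 ≈ 0.518 day. Both variables precede delivery and need no cohort label, so blinding is unaffected. If the opening date also bounds deliveries, trimming both ends would keep about 85% in the simulation, which favours a sensitivity analysis in that case.

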1.6. Overview of proposed analyses

EG will analyze the primary, secondary, and exploratory outcomes for the trial data. LH will generate data and run models as needed so that EG remains blinded to the identity of each cohort (see section 2.5).

The primary analyses will be multiple linear regression models estimating average treatment effects of the MHP app. Secondarily, dose-response models will be created for the primary and secondary outcomes in order to understand the moderating effects of app usage.

The primary and secondary outcomes for the study will come from electronic health record (EHR) data for trial participants. Given the source and the nature of care for women who deliver in the UPMC system, few outcome data are missing data. As such, imputation will not be used to account for missing outcome data. Instead, participants will be excluded from analyses, if their outcome data is missing for an outcome measure.

As a sensitivity analysis, propensity score matching will be used to create similar cohorts of participants, excluding participants whose propensity scores are outside the overlap in the covariate distributions for the covariates that predict downloading the MHP app (see section 3.1.5). We will calculate average treatment effects for these matched subsets of participants. Inverse probability of treatment weighting will be used as an additional sensitivity analysis to account for the potential lack of overlap in covariate distributions between the study cohorts.

2. Data analysis plan – data description

2.1. Recruitment and representativeness of recruited patients

A flow diagram will describe the flow of participants from prescription of the MHP app into the MHP and usual care cohorts. The final diagram will be similar to Figure 1 below.

[figure not shown]

Figure 1. Flow of trial participants from app prescription to cohort inclusion

2.2. Baseline comparability of MHP versus usual care cohorts

Tables will be used to describe demographic and baseline measures for the MHP and usual care cohorts. Means and standard deviations will summarize continuous variables. Proportions and frequencies will summarize categorical variables. Based on STROBE guidelines, the statistical significance of differences between the cohorts will not be estimated, as this is not an appropriate method for identifying covariates that may have affected outcomes.

2.3. Treatment Usage

At its current stage of development, the MHP app does not prescribe a set dosage, specifying how often patients should interact with it in order to have desired effects. As such, this study investigates app usage as a mediator of the outcome, rather than comparing users who did and did not meet a predetermined dosage.

We will assess the following aspects of usage: how soon after receiving the prescription participants initiated app use (in days); how soon they discontinued app use prior to delivery (in days since initiation); the percentage of days they used it overall (within the usage period); and the percentage of weeks they used it at least once (within the usage period). See Appendix A for details on these use metrics.

2.4. Loss to follow-up and other missing data

Given data-sharing constraints with UPMC, outcome data is available only for participants who delivered at UPMC hospitals. LH will report how many people downloaded the app and did not deliver at UPMC. This will allow us to estimate the percentage of participants lost due to delivering out of the system.

For included participants, there is a very little missing data for the primary measure (80/13752=0.06%). We will assume that such data is missing at random and exclude participants whose data is missing for a measure from analyses involving that measure. There is no missing data for the secondary measures. The same practice will be followed for the exploratory outcomes. No imputation will be done for any outcome measures.

Missing categorical values for baseline covariates (baseline disease information and demographics) will not be imputed, but treated as an additional category. Continuous variables missing less than 5% of the data will be imputed with the median value for that variable. Two continuous baseline covariates are missing more than 5% of data ADI_NATRANK (1330/13752=9.7%) and PREGRAVID_WEIGHT (1318/13752=9.6%). For these two variables, scatterplots and Little's test will be used to investigate if the data is missing completely at random (MCAR), missing at random (MAR), or missing not at random (MNAR) on 20% of the unblinded data. If the data appears to be MCAR or MNAR, median imputation will be used. If the data is MAR, multiple imputation will be used. If multiple imputation is needed, LH will generate data for the missing values so that EG remains blinded. For all missing data, we will conduct

sensitivity analyses, repeating analyses of primary and secondary outcomes using imputed values two standard deviations above and below the median. See Appendix A for the full list of collected baseline covariates.

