3.1.1. Analysis of primary outcomes

The difference in gestational weeks at birth will be evaluated using a linear effects model accounting for confounders of preterm birth, as measured at baseline. We estimate that about 57 out of 12,344 deliveries are for a second pregnancy for participants included in the sample given that 0.464% of participants who downloaded the app had two deliveries in the sample. We have included these women in the sample because we cannot exclude similar women in the usual care cohort given limitations in our data. Likewise, we cannot account for random effects of multiple deliveries using a mixed effects model.

Baseline study variables will be included as confounders in the model if (a) the literature has identified the variable as a confounder of preterm birth risk and (b) they might plausibly have influenced participants' decision to download the app. If, for a variable, the evidence on condition (a) is inconclusive and condition (b) is possible, we will examine the data and include the variable if it passes a 10% change-in-estimates threshold for the outcome or for the likelihood of downloading the app. The change-in-estimate will be calculated by adding each study variable to the model from the literature individually. Only baseline variables will be evaluated as potential confounders, as they could not have been affected by use of the app.

We will report the results of two models for each outcome, one using only confounders identified in the literature and one adding confounders identified empirically (Appendix A). Including fewer confounders will reduce the likelihood that the average treatment effect applies only to an unrepresentative subset of the population. Including additional confounders will reduce the likelihood of statistical bias in estimating the average treatment effect.

The dataset contains many known confounders of preterm birth that could be included in the model including:

- Previous preterm birth (3)
- Race (3)
- Low body-mass index (3,4)
- Insurance type (5)
- Area deprivation index (6)
- Multiple gestations (3)
- Previous spontaneous abortions (7)
- Hypertension (3)
- Diabetes (3)
- Tobacco use (3)

There are also many known predictors of preterm birth that are not in the EHRs, hence not available for this study. They include educational attainment, marital status, interpregnancy interval, relatives who delivered preterm, and genetic predictors of preterm birth (3).

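### Section 2.4 chooses the imputation method for two confounder variables by a MAR/MNAR distinction that its tools cannot make, and several of its missing-data figures need correction

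*SAP*

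**What the plan says.** Section 2.4 sets the imputation rule. Continuous baseline covariates with less than 5% missing get the median. Two exceed that: ADI_NATRANK at 1330/13752 = 9.7%, and "PREGRAVID_WEIGHT (1318/13752=9.6" per cent). For these two, scatterplots and Little's test on the unblinded 20% are to show whether the data are MCAR, MAR or MNAR. Then: "If the data appears to be MCAR or MNAR, median imputation will be used", and "If the data is MAR, multiple imputation will be used". The section adds sensitivity analyses that repeat the primary and secondary analyses with imputed values two SDs above and below the median.

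On outcomes, the section says that for included participants "there is a very little missing data for the primary measure (80/13752=0.06" per cent). It continues with "There is no missing data for the secondary measures" and "No imputation will be done for any outcome measures".

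On the sample, section 1.5 says "The final sample has 12,344 deliveries", and section 3.1.1 uses the same total: "We estimate that about 57 out of 12,344 deliveries are for a second pregnancy".

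**The concern.** The two variables matter. Section 3.1.1 lists area deprivation index and low body-mass index among the known confounders of preterm birth. Appendix A has flags for obesity and morbid obesity but none for low BMI, so low BMI has to be built from PREGRAVID_WEIGHT and height. A record filled with the median weight would rarely be classed as low BMI. How these values are filled therefore affects confounder adjustment in roughly one record in ten, in an observational comparison that depends on that adjustment.

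The rule makes the method depend on a distinction that the data cannot supply. It also assigns the cruder method, a single constant, to MNAR, which is the hardest case.

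The figures around the rule have lesser faults. One percentage does not match its fraction. The denominator is not the analysed sample. The statement that the secondary measures are complete sits beside counts that imply otherwise for two derived outcomes.

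**Working it through.** **Imputation rule.** Little's test has MCAR as its null hypothesis. It leaves two situations:

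- Not rejected: MCAR is compatible with the data, but so is MNAR unrelated to the observed variables. The rule gives median imputation either way.
- Rejected: the data may be MAR or MNAR. The rule now prescribes different methods, and neither the test nor a plot of observed values can say which applies, because the difference lies in the unobserved values.

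A simulation illustrates this. Its settings are assumptions, not plan figures: n = 0.2 × 12,344 ≈ 2,469; weight and one complete covariate, bivariate normal; about 10% of weights missing; log-odds slope of 0.5 per SD; Little's test on 1 df at 5%; 1,500 runs per setting. Rejection rates were:

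- MCAR: 5–6%.
- MAR (missingness depends on the covariate): 100%.
- MNAR (missingness depends on weight): 4.9%, 10.6%, 56.3% and 94.5% at weight–covariate correlations of 0, 0.1, 0.3 and 0.5.

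MNAR data can thus look like MCAR or like MAR. Filling 9.58% of a covariate with one constant near its mean also reduces its SD to √(1 − 0.0958) = 0.951 of the true value. That describes the covariate, not the treatment effect.

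**The percentage.** The companion figures reproduce: 1330/13752 = 9.67% and 1318/13752 = 9.58%. The primary-outcome figure does not: 80/13752 = 0.58%. With the sample size from section 1.5, 80/12344 = 0.65%. A count of 8 would give 8/13752 = 0.058%, so either the percentage or the count is misprinted.

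The consequence is small. With SD 10 days and a two-sided 5% level (sidedness is assumed; the SAP does not state it), the detectable difference at 80% power is (1.960 + 0.842) × √(1/7147 + 1/5197) × 10 = 0.51 day, which matches section 1.5. Removing 80 deliveries in proportion lowers power at 0.51 day from 79.9% to 79.6%.

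**The denominator.** 7147 + 5197 = 12,344, and 13,752 − 12,344 = 1,408 (10.2% of 13,752). If the 12,344 are a subset of the 13,752, missingness within them lies between 0% (both 1,330 and 1,318 are below 1,408) and these maxima:

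- ADI_NATRANK: 1330/12344 = 10.8%.
- PREGRAVID_WEIGHT: 1318/12344 = 10.7%.

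The 5% threshold on 12,344 is about 617 records. To fall to it, 1330 − 617 = 713 (51%) of the 1,408 dropped records would have to lack ADI_NATRANK, or 1318 − 617 = 701 (50%) would have to lack PREGRAVID_WEIGHT. Both variables probably stay above 5%, but the SAP does not show it.

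**The secondary outcomes.**

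- Outcome 1, preterm birth, is delivery before 37 weeks (section 1.1.2). The only gestational age at birth in Appendix A is EST_GEST_AGE_DAYS, the primary outcome, missing for 80.
- Outcome 7, sufficient gestational weight gain, depends on pregravid BMI (the footnote on the 2009 guidelines) and so on PREGRAVID_WEIGHT, missing for 1,318.

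**The case against.** The strongest defence of the rule is the planned repetition with values two SDs above and below the median. That is a direct stress test for MNAR and deserves credit. It shows how far the results could move, but it does not supply a criterion for choosing the main method. It is also fair that standard multiple imputation does not resolve MNAR, and that the simulation uses one complete covariate where Appendix A lists dozens and does not model the scatterplots. The argument does not rest on the simulation: observed data cannot separate MAR from MNAR whatever the parameters.

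Three stronger readings are tempting, and the SAP does not support them.

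- A reader might infer that 13,752 is simply the wrong denominator. Figure 1 traces participants from prescription to cohort, was not available in the text reviewed, and may explain the difference. The wording about included participants sits awkwardly with a pre-exclusion count, but that does not prove an error.
- A reader might infer that the secondary data are incomplete in general. Appendix A labels gestational age as primary and pre-pregnancy weight as a baseline covariate, so the fields it labels secondary may all be complete. The contradiction is shown only for two derived outcomes.
- A reader might infer that up to 9.6% of outcome 7 values will be built from one median weight. That means reading past the ban on outcome imputation in section 2.4 and the exclusion of missing outcomes in sections 1.6 and 3.1. What remains is that the SAP does not say how the ban applies when an outcome's input is itself an imputed covariate.

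**Conclusion.** The imputation rule is badly fixed and should be changed before the analysis. It governs two variables behind listed confounders, at 9.7% and 9.6% missing on the SAP's own denominator. Its criterion cannot separate the cases it is meant to separate, and its treatment of MNAR has no justification. The two-SD analyses reduce the exposure. Nothing here shows the size or direction of any effect on the treatment estimate.

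The remaining points are corrections of fact. The misprint is certain as arithmetic (0.58% against 0.06%), though which number is wrong is not known, and its effect on the primary conclusion is small. The fractions have not been shown to describe the 12,344 deliveries analysed. The completeness statement fails for two of the nine secondary outcomes as derived, on the assumption that each is computed from the Appendix A variables named above.

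**What to change.** 1. Use multiple imputation for ADI_NATRANK and PREGRAVID_WEIGHT as covariates whatever Little's test shows. Keep the analyses at two SDs above and below the median as the MNAR sensitivity check.
2. Confirm the count of 80 against the data and correct whichever figure is wrong.
3. Restate the missing-data fractions and the 5% threshold check on the 12,344 deliveries, and explain how 13,752 relates to them.
4. Replace the completeness statement with missing counts for outcomes 1 and 7. State that, under the existing ban on outcome imputation, outcome 1 is missing when gestational age is missing and outcome 7 is missing when its inputs are missing, so that an imputed pre-pregnancy weight is never used to build outcome 7.

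The cost is SAP wording, a recount, and slightly more analysis work. Section 2.4 already provides for multiple imputation under MAR, with a team member generating the values so that the primary statistician stays blinded. The stated missingness may become less favourable.
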